**Research Question:**

Dose statins give survival benefits in breast cancer patients with abnormal lipid metabolism?

**Specific aims:**

To evaluate the survival benefits of statins in breast cancer patients with dyslipidemia (low and medium risk of ASCVD).

**Significance:**

In 2015, there were about 272,000 new cases of female breast cancer and 70,700 deaths in China [1]. The peak incidence of breast cancer among women in East Asia is 45-54 years old. In China, 69.75% of all breast cancer cases are women over 45 years old. Therefore, more than half of breast cancer patients are in perimenopause or menopause at the time of onset[2]. According to the US surveillance, epidemiology and final results database, cardiovascular events in breast cancer patients aged over 66 were the leading cause of death, accounting for 15.9%, and breast cancer-related deaths accounted for 15.1% [3-4]. The estrogen level of postmenopausal women with breast cancer is

significantly reduced by both ovarian dysfunction and drug treatment. Common dyslipidemia and the risk of cardiovascular disease are also increased. Cardiovascular disease-related deaths have jumped to the top of these deaths except for breast cancer. Premenopausal women also suffer from dyslipidemia during adjuvant therapy. However, clinicians often neglect the risk of dyslipidemia and cardiovascular disease.

Adjuvant endocrine therapy is an important part in the treatment of breast cancer. Estrogen in postmenopausal women mainly comes from tissues other than ovaries, such as fat, muscle, skin and so on. It is formed by aromatization of androstenedione and testosterone. Aromatase is an indispensable rate-limiting enzyme in this process. Aromatase inhibitors can block the main source of estrogen in postmenopausal breast cancer patients, so as to control the growth of breast cancer cells and treat tumors [5-8]. The third generation of aromatase inhibitors has become the first choice of adjuvant therapy for estrogen receptor-positive, early postmenopausal breast cancer patients. At present, the recommended time for use is 5 to 10 years [7].

Based on current epidemiological and clinical studies, it is practical and reasonable to set appropriate cholesterol-lowering target values according to patients' overall cardiovascular risk level. For low, medium and high risk patients without ASCVD, the LDL\_C target values recommended by the guidelines for prevention and treatment of adult dyslipidemia in China are < 4.1, 3.4 and 2.6 mmol/L, respectively (corresponding non-HDL\_C target values are LDL\_C + 0.8 mmol/L, cholesterol conversion unit: 1 mmol/L = 1 mg/dl \* 0.0259), beyond which lifestyle interventions and (or) drug therapy should be initiated. These suggestions are based on the epidemiological characteristics of dyslipidemia in Chinese residents and the available clinical evidence, which are the basic criteria for current lipid management. Based on cholesterol theory and many new research results published in recent years, it is possible to further reduce the cardiovascular risk of patients by continuing to reduce LDL\_C or non-HDL\_C levels to a certain extent. At present, the target of blood lipid intervention for breast cancer patients lacks evidence-based medical support. Therefore, the Chinese consensus recommends that cholesterol [9] be controlled more strictly for postmenopausal women, referring to the expert recommendations of the prevention and treatment of dyslipidemia in the 2014 China Cholesterol Education Program. It is suggested that the ideal level of LDL\_C in postmenopausal breast cancer patients without risk factors should be < 3.4 mmol/L.

However, the consensus of Chinese experts on the management of dyslipidemia in early postmenopausal breast cancer published in 2017 has not made clear recommendations on which patients should use lipid-lowering drugs and how much to use. Especially in clinical practice, the control of blood lipid is a grey area for low-risk patients with ASCVD. In recent years, studies have shown that statins can reduce the recurrence and metastasis of breast cancer and improve the overall survival of breast cancer patients [10-13]. Therefore, this study is an active effort to seek a survival benefit program for patients at low and medium risk of ASCVD.

## **Methods:**

### Overview of design:

A randomized, open, blank controlled, single-center clinical trial was conducted to compare the survival benefits of statins in breast cancer patients with dyslipidemia (low and medium risk of ASCVD). The control group used dietary intervention instead of statins. The main endpoint was 5 years DFS. The subjects were breast cancer patients. In this study, 348 patients were randomly divided into two groups according to patients' wishes and written informed consent. The experimental group: control group = 1:1. Subjects were screened and administered continuously until the disease progressed and the toxicity was intolerable. Informed consent was withdrawn or the researcher decided that the drug must be discontinued.

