**Abstract:**

This is a randomized clinical trial from March 28st 2019 to March 28st 2024. The purpose of this study is to evaluate the survival benefits of statins in breast cancer patients with abnormal lipid metabolism. Consecutive samples will be enrolled based on inclusion and exclusion criteria. They will be grouped randomly into intervention group or control group after informed consent. A third group independent from research team will be in charge of randomization. In this study, 348 patients were randomly divided into two groups according to patients' wishes and written informed consent. The experimental group: control group = 1:1. Patients in both groups will undergo breast cancer treatment. The experimental group used statins, while the control group used dietary intervention instead of statins. The main endpoint was 5 years DFS. The subjects were breast cancer patients. For statistical analysis, t-test will be used between two different groups. Estimated sample size will be calculated using t-test. Log rank test was used with survival curve based on Kaplan Merier method and 95% confidence interval of median survival time. Data and Safety Monitoring Board will periodically review, evaluate and give recommendations to this study in various aspects.

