#### Plans for sampling, recruiting and retaining subjects:

- Sample type: Convenience sample
- Sampling procedures: Convenience sampling will be used to enroll a cohort of breast cancer patients with dyslipidemia (low and medium risk of ASCVD), and randomly separate them into two groups. We prepare to use SPSS software to do the randomly separation. Experimental group used statins, the other one used dietary intervention instead of statins.
- Recruitment method: When patients presented our hospital diagnosed of breast cancer with dyslipidemia (low and medium risk of ASCVD), we will review these patients' medical records to find out the potential subjects for this study according to the inclusion and exclusion criteria. The eligible subject who is willing to participate in this study will be enrolled and consented. They will be randomly (using SPSS software) divided into 2 groups. One is statins group, the other one is control group.

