#### Measurements:

- Predictor variables:

The predictor variable we are assessing is whether use statins. According to which, we established the intervention group and control group.

- Outcome variables:

The primary outcome: DFS (disease free survival) rate

Secondary outcome: OS (overall survival) rate

- Potential confounders:

Since this protocol is an RCT (randomly clinical trial) on survival benefits between statins group and control group, it will balance the confoundings in it, such as age, slight pathology difference, tumor size difference, lymph node status difference, tumor grade difference, and the different surgeons between the 2 groups.

- Plans for randomization, blinding, run-in period as needed:

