#### 1) Randomization

We prepare to use SPSS software to do the randomly separation. According to the inclusions and exclusions, once we find the right patient, we will put the name in computer. The computer will randomly tell which group the patient will be in. After explanations to the patients, and receiving the patient agreements, we will sign the informed consent with them.

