#### 4) Stratified blocked randomization

In clinical practice, different molecular subtypes do relate to different prognosis and treatment. So we would like to stratify blocked randomization according to molecular subtype. Previous study [12] show that the proportion of luminal A, luminal B, Her-2 positive and triple-negative are 32.73%, 47.01%, 5.71%, 14.55%. And we will do subgroup analysis.

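### The Abstract and Overview of design, read literally, make patients' wishes a basis for the arm, which contradicts the allocation by chance described elsewhere; the plan does not resolve this

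*Combined protocol and SAP*

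**What the plan says.** The same sentence appears in the Abstract and in Methods, Overview of design: "348 patients were randomly divided into two groups according to patients' wishes and written informed consent". Both places add a 1:1 ratio.

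Other text leaves the arm to chance:

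- Abstract: "A third group independent from research team will be in charge of randomization", and "They will be grouped randomly into intervention group or control group after informed consent".
- Plans for sampling, recruiting and retaining subjects: "The eligible subject who is willing to participate in this study will be enrolled and consented". SPSS then divides these patients into the two groups.
- Randomization: "The computer will randomly tell which group the patient will be in".
- Stratified blocked randomization: "So we would like to stratify blocked randomization according to molecular subtype".

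Under Measurements (potential confounders), the plan relies on randomisation for comparability: "it will balance the confoundings in it", naming age, pathology, tumour size, nodal status, grade and surgeon. The tests named in the Abstract are the t-test and the log-rank test, with no adjustment stated. No section defines wishes, says what happens when a patient declines her arm, or defines analysis by assigned arm.

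**The concern.** Whether chance or choice sets the arm decides whether the DFS comparison is randomised. The sentence lists wishes in addition to written consent and attaches both to the division into groups. A site following it as written could let a preference for a statin or for diet influence the arm. Such a preference could plausibly be related to age, comorbidity, health behaviour and perceived risk of recurrence, and through them to DFS. With unadjusted tests, any resulting imbalance would pass straight into the DFS difference and could not be told apart from a drug effect. Stratifying by molecular subtype protects the comparison only if the list decides the arm.

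Two other parts of the plan leave the gap open. The Overview of design calls the trial open, and the Randomization text puts the computer's answer before the explanation and signed consent, so an arm could be known while a patient is still deciding. Exclusion criteria 12 and 13 (failure to complete one cycle; serious departure from the prescribed treatment) can be judged only after treatment has begun. They could be used to remove a randomised patient who does not follow her arm.

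**Working it through.** The plan gives no figure for this point, so the main check is textual.

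**Step 1. The texts side by side.**

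| Place | What settles the arm |
|---|---|
| Abstract and Overview of design (same sentence) | Chance, together with patients' wishes and consent |
| Abstract, earlier sentences | Chance, after consent, run by an independent group |
| Plans for sampling and recruiting | SPSS, after willingness and consent |
| Randomization | The computer, before explanation and consent |
| Stratified blocked randomization | Blocks within molecular subtype |

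If wishes means willingness to take part, the first row agrees with the others on what decides the arm. If it means preference for an arm, it does not. The recruitment text supports the first meaning; the grammar of the sentence permits the second. Nothing in the plan chooses between them.

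**Step 2. What placement by preference would do (illustration only).** The documents give none of p, D, m or the split of wishes. Assume a share p of patients is placed by wish, wishes split evenly, overall 5-year DFS is m, DFS differs by D between those wishing for a statin and those wishing for diet, and there is no drug effect.

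- Statin arm: (1 − p)m + p(m + D/2)
- Control arm: (1 − p)m + p(m − D/2)
- Difference: p × D

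D may take either sign, so the distortion could mimic a benefit or hide one.

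**Step 3. Effect on the false-positive rate.** From the plan: 348 patients at 1:1, so 348/2 = 174 per arm; two-sided α = 0.05. Assumed: m = 85%.

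- Standard error = √(2 × 0.85 × 0.15/174) = 0.0383.
- Type I error = 1 − Φ(1.96 − pD/SE) + Φ(−1.96 − pD/SE).
- Example, p = 20% and D = 10 points: pD = 0.02 and pD/SE = 0.52, giving 8.2%.

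| p | D = 5: spurious difference (points) | Type I error | D = 10: spurious difference (points) | Type I error |
|---|---|---|---|---|
| 0% | 0 | 5.0% | 0 | 5.0% |
| 10% | 0.5 | 5.2% | 1 | 5.8% |
| 20% | 1 | 5.8% | 2 | 8.2% |
| 30% | 1.5 | 6.8% | 3 | 12.3% |
| 50% | 2.5 | 10.0% | 5 | 25.7% |

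The yardstick is the 10-point DFS difference in Statistical issues. D = 10 was chosen to equal that target, so the results as a fraction of the target (10% to 50% for p = 10% to 50%) reflect that choice.

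**The case against.** The strongest reply is that the sentence itself says the division was random and joins wishes to consent, so its natural sense is that willing, consenting patients were randomised. The recruitment text sets out exactly that sequence. The disputed words occur only in two summary texts, and none of the sections describing how recruitment and allocation work gives preference any role in choosing the arm. The case p = 0 is what those sections describe. Even at p = 10% the illustrated error rate is close to nominal.

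Much of this stands. A reader might infer that patients chose their arm, or were moved to the other arm after the computer's answer. The documents do not support that: no section describes placement by preference or switching, although none forbids them. The absence of a rule for analysis by assigned arm would also be a gap without this sentence.

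What remains is that the milder meaning is nowhere stated. Written consent already covers willingness, so the extra word invites the other reading, and nothing elsewhere in the plan fixes the assigned arm against preference.

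**Conclusion.** The point holds as an unresolved contradiction about the basis of allocation. It should be corrected because the rule, if followed as written, would bias an unadjusted DFS comparison, and later analysis could not reliably repair that.

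A reader might go further and conclude that the randomised comparison is already broken. That is not supported: it depends on how many patients, if any, were placed by preference and on how their prognosis differed, and the documents give neither. The size is p × D, zero if no one was placed by wish. The illustrated 1 to 5 points rest wholly on the assumed p, the even split of wishes and D = 10; the error rates also assume 85% DFS. Small shares would matter little and large shares a great deal.

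**What to change.** 1. In the Abstract and the Overview of design, delete the reference to patients' wishes. State that patients who consent to assignment to either arm are then allocated 1:1 by the independent stratified blocked list.
2. State that DFS and OS are analysed by randomised arm, including patients who later decline or change treatment, and that exclusion criteria 12 and 13 are not used to remove randomised patients from that analysis. The Appendix form already has a statin entry at baseline and at every visit to 5 years, which can record actual use.
3. For patients already enrolled, compare the arm recorded at entry with the allocation list and report mismatches. The check has limits: it cannot detect preference that acted before the list entry, and a mismatch in statin use alone does not separate misallocation from non-adherence.

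The cost is a few sentences and one reconciliation. Patients with a fixed preference would not be randomised, so recruitment may be slightly slower. Analysis by randomised arm also dilutes the effect if patients change treatment. Assuming 90% against 80% DFS, the plan's 157 per arm and equal switching s in both arms, the difference becomes 10 × (1 − 2s) points. Power falls from 70% with no switching to 61%, 51% and 32% at s = 5%, 10% and 20%. That loss is the price of keeping the comparison randomised.

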### Study subjects:

- Target population: Breast cancer patients with dyslipidemia (low and medium risk of ASCVD).
- Accessible population: Breast cancer patients with dyslipidemia (low and medium risk of ASCVD).
- Selection criteria: Well suited to the research question, representative of target populations and available, representative of accessible populations and easy to study. They should be breast cancer patients.
  - 1) Diagnosed as invasive breast cancer, it has been treated surgically, confirmed by histology, cytology or imaging.
  - 2) Female patients (35-75 years old);
  - 3) The low-risk patients with ASCVD;
  - 4) Signed written informed consent approved by IRB or IEC
- Exclusion criteria:
  - 1) The subjects were pregnant or lactating.
  - 2) Pregnancy test positive (urine or serum) in women with potential pregnancy within 7 days before administration.
  - 3) Other invasive tumors (including the second primary breast cancer) may affect the evaluation of outcomes and the compliance of schemes, but subjects who have been cured and survived disease-free for at least five years can be selected.
  - 4) Patients with chronic underlying liver diseases who have abnormal liver function and/or clinical manifestations:  
Serum total bilirubin > 2.5 \*ULN; or INR > 1.5 although there was no increase in bilirubin  
Serum ALT or AST > 3 \*ULN;  
Alkaline phosphatase > 2.5 \*ULN;  
Elevated ALT or AST may gradually recover, but with progressively increased fatigue, nausea and vomiting, fever, right upper abdominal pain or tenderness.
  - 5) Extremely high risk ASCVD patients Including acute coronary syndrome (ACS), stable coronary heart disease, revascularization, ischemic cardiomyopathy, ischemic stroke, transient ischemic attack, peripheral atherosclerosis, etc.

6) High-risk ASCVD patients (in accordance with one of the following circumstances):

LDL-C > 4.9 mmol/L or TC > 7.2 mmol/L Diabetic patients with 1.8 mmol/L < LDL-C < 4.9 mmol/L (or) 3.1 mmol/L < TC < 7.2 mmol/L and age < 40 years

The 10-year risk of ASCVD was moderate and younger than 55 years old. The remaining life risk was assessed. Those with any of the following two or more risk factors are defined as high risk:

Systolic or diastolic blood pressure (> 160 mmHg) or (> 100 mmHg)

a) Non-HDL-C > 5.2 mmol/L (200 mg/dl)

b) HDL-C < 1.0 mmol/L (40 mg/dl)

c) BMI > 28 kg/m^2 Smoking

7) In the abnormal group of simple TG (triglyceride), TG (> 5.7 mmol/L)

8) Other serious diseases, including:

Congestive heart failure (NYHA grade II, III, IV); dyspnea at rest or requiring oxygen therapy; severe infection; uncontrolled diabetes mellitus;

9) If there are serious mental or mental disorders, it is estimated that the subjects' compliance to participate in this study is not strong.

10) Drug allergies to research drugs are known.

11) Participated in other drug clinical trials in the past 30 days.

12) Failure to complete at least one cycle of clinical trials based on this protocol, and failure to evaluate safety and effectiveness.

13) Serious violation of this study program, not in accordance with the prescribed dose, method and course of treatment.

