Appendix

Statins VS. Dietary Intervention on Breast Cancer Patients

Date: --/-- [dd / mm / yyyy]

Name: \_\_\_\_\_

Address: \_\_\_\_\_

ID No.: \_\_\_\_\_

Medical record No.: \_\_\_\_\_

Sex: Female

Date of birth: --/-- [dd / mm / yyyy]

Pathology: \_\_\_\_\_ molecular type \_\_\_\_\_

T \_\_\_\_\_ N \_\_\_\_\_ M \_\_\_\_\_

ER \_\_\_\_\_ PR \_\_\_\_\_ Her-2 \_\_\_\_\_

Ki-67 \_\_\_\_\_ P53 \_\_\_\_\_

Date of surgery \_\_\_\_\_ surgery type \_\_\_\_\_

Other treatment \_\_\_\_\_

Baseline: date \_\_\_\_\_ statin \_\_\_\_\_

LDL-C \_\_\_\_\_ TC \_\_\_\_\_ TG \_\_\_\_\_ ALT \_\_\_\_\_ CK \_\_\_\_\_ Fatty Liver \_\_\_\_\_

1 month follow-up: date \_\_\_\_\_ statin \_\_\_\_\_

LDL-C \_\_\_\_\_ TC \_\_\_\_\_ TG \_\_\_\_\_ ALT \_\_\_\_\_ CK \_\_\_\_\_ Fatty Liver \_\_\_\_\_

3 month follow-up: date \_\_\_\_\_ statin \_\_\_\_\_

LDL-C \_\_\_\_\_ TC \_\_\_\_\_ TG \_\_\_\_\_ ALT \_\_\_\_\_ CK \_\_\_\_\_ Fatty Liver \_\_\_\_\_

6 month follow-up: date \_\_\_\_\_ statin \_\_\_\_\_

LDL-C \_\_\_\_\_ TC \_\_\_\_\_ TG \_\_\_\_\_ ALT \_\_\_\_\_ CK \_\_\_\_\_ Fatty Liver \_\_\_\_\_

RT (recurrence time)\_\_\_\_\_

Other event\_\_\_\_\_

1 year follow-up: date\_\_\_\_\_statin\_\_\_\_\_

LDL-C\_\_\_\_\_TC\_\_\_\_\_TG\_\_\_\_\_ALT\_\_\_\_\_CK\_\_\_\_\_Fatty Liver\_\_\_\_\_

RT (recurrence time)\_\_\_\_\_

Other event\_\_\_\_\_

1.5 year follow-up: date\_\_\_\_\_statin\_\_\_\_\_

LDL-C\_\_\_\_\_TC\_\_\_\_\_TG\_\_\_\_\_ALT\_\_\_\_\_CK\_\_\_\_\_Fatty Liver\_\_\_\_\_

RT (recurrence time)\_\_\_\_\_

Other event\_\_\_\_\_

2 year follow-up: date\_\_\_\_\_statin\_\_\_\_\_

LDL-C\_\_\_\_\_TC\_\_\_\_\_TG\_\_\_\_\_ALT\_\_\_\_\_CK\_\_\_\_\_Fatty Liver\_\_\_\_\_

RT (recurrence time)\_\_\_\_\_

Other event\_\_\_\_\_

2.5 year follow-up: date\_\_\_\_\_statin\_\_\_\_\_

LDL-C\_\_\_\_\_TC\_\_\_\_\_TG\_\_\_\_\_ALT\_\_\_\_\_CK\_\_\_\_\_Fatty Liver\_\_\_\_\_

3 year follow-up: date\_\_\_\_\_statin\_\_\_\_\_

LDL-C\_\_\_\_\_TC\_\_\_\_\_TG\_\_\_\_\_ALT\_\_\_\_\_CK\_\_\_\_\_Fatty Liver\_\_\_\_\_

RT (recurrence time)\_\_\_\_\_

Other event\_\_\_\_\_

3.5 year follow-up: date\_\_\_\_\_statin\_\_\_\_\_

LDL-C\_\_\_\_\_TC\_\_\_\_\_TG\_\_\_\_\_ALT\_\_\_\_\_CK\_\_\_\_\_Fatty Liver\_\_\_\_\_

4 year follow-up: date\_\_\_\_\_statin\_\_\_\_\_

LDL-C\_\_\_\_\_TC\_\_\_\_\_TG\_\_\_\_\_ALT\_\_\_\_\_CK\_\_\_\_\_Fatty Liver\_\_\_\_\_

RT (recurrence time)\_\_\_\_\_

Other event\_\_\_\_\_

4.5 year follow-up: date\_\_\_\_\_statin\_\_\_\_\_

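### The entry criteria do not require patients to be free of disease at randomisation, so patients with metastatic, residual or recurrent breast cancer can enter a trial whose primary endpoint is 5-year disease-free survival

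*Combined protocol and SAP*

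**What the plan says.** Under Study subjects, inclusion item 1 reads "Diagnosed as invasive breast cancer, it has been treated surgically, confirmed by histology, cytology or imaging". The other three inclusion items cover sex and age, ASCVD risk, and consent. Among the 13 exclusions, the only one that uses the idea of being disease-free is item 3, which begins "Other invasive tumors (including the second primary breast cancer) may affect the evaluation of outcomes and the compliance of schemes" and so concerns tumours other than the index cancer. The population is described as "Target population: Breast cancer patients with dyslipidemia (low and medium risk of ASCVD"), with no limit to early or non-metastatic disease.

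The recruitment text says "When patients presented our hospital diagnosed of breast cancer with dyslipidemia (low and medium risk of ASCVD), we will review these patients' medical records" against those same criteria. The Run-in design paragraph mentions a diagnostic evaluation but gives it no staging content.

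On the endpoint, Overview of design states "The main endpoint was 5 years DFS" and Measurements states "The primary outcome: DFS (disease free survival) rate". Neither gives an event list or a time origin. The Appendix form collects the outcome as "RT (recurrence time"). The treatment text in Overview of design reads "Subjects were screened and administered continuously until the disease progressed and the toxicity was intolerable".

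**The concern.** DFS presupposes that the patient is free of disease when the clock starts. The entry rule does not secure this. Having had surgery narrows the population but does not make it disease-free. A woman whose primary tumour was removed in the presence of metastases, one whose resection was incomplete, and one who has relapsed after an earlier operation all meet item 1, and no exclusion stops them. No limit on time since surgery is set.

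The plan has no rule for such a patient, and both obvious ways of handling her do harm. If she counts as an event at or near day 0, she does so whichever arm she is in, and the arms are pulled together. If she is taken out later, that is a post-randomisation exclusion in a trial described as open, where knowledge of the arm could influence who is removed. In either case the 5-year rate no longer measures the reduction in recurrence on which the 10% target under Statistical issues rests. Randomisation is stratified by molecular subtype only, so a chance imbalance in disease status between the arms is not controlled by design.

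**Working it through.** **Step 1: is the criterion supplied anywhere?**

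| Place | What it contributes |
|---|---|
| Inclusion 1 | Invasive cancer, surgically treated; no M0, completeness of resection or recurrence status |
| Inclusion 2 to 4 | Sex and age, ASCVD risk, consent |
| Exclusion 3 | Other invasive tumours, including a second primary; not the index cancer |
| Remaining exclusions | Nothing on metastasis, residual disease or recurrence |
| Sampling and recruitment | Record review against the same list |
| Run-in design | Diagnostic evaluation, content not stated |
| Appendix form | T, N and M, pathology, surgery date and type are recorded, but no value is a condition of entry |

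The criterion is absent throughout.

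**Step 2: the plan's own figures.** The target is a 10% difference in DFS, with 157 patients per group and 348 in total after 10% dropout. No control-arm DFS rate is given, nor any proportion with disease at entry. The dropout step reproduces within rounding: 2 × 157 / 0.9 = 348.9. The 157 does not follow from its stated inputs: 2 × (1.960 + 1.282)² / 0.1² gives about 2,102 per group. That is a separate matter. Here 157 is used only as the plan's number per group.

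**Step 3: illustration of dilution.** The following are assumptions, not figures from the documents: 5-year event rates p (control v statin), and a fraction k of patients not disease-free at entry, the same in both arms and all counted as events.

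- Observed event rate = p(1 − k) + k
- Observed difference = 10 points × (1 − k)
- Share of events that carry no information = k / mean of the two observed rates

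For 20% v 10% and k = 5% (0.05 × 348, about 17 patients):

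- Control: 0.20 × 0.95 + 0.05 = 0.240
- Statin: 0.10 × 0.95 + 0.05 = 0.145
- Difference: 9.5 points. Relative risk: 0.145 / 0.240 = 0.60
- Uninformative share: 0.05 / 0.1925 = 26%

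| k | Observed rates | Difference (points) | Relative risk | Uninformative events |
|---|---|---|---|---|
| 0 | 20.0% v 10.0% | 10.0 | 0.50 | 0 |
| 3% | 22.4% v 12.7% | 9.7 | 0.57 | 17% |
| 5% | 24.0% v 14.5% | 9.5 | 0.60 | 26% |
| 10% | 28.0% v 19.0% | 9.0 | 0.68 | 43% |

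**Step 4: effect on power.** This uses a two-sided 5% test of two proportions with 157 per arm, under the same assumptions.

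| Assumed rates | k = 0 | k = 3% | k = 5% | k = 10% |
|---|---|---|---|---|
| 15% v 5% | 84% | 73% | 67% | 53% |
| 20% v 10% | 70% | 62% | 57% | 47% |
| 30% v 20% | 53% | 49% | 46% | 40% |

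Power falls faster than the difference does, because the added events also raise the variance of both rates. The direction is the same in every row. The amount depends on rates that the plan does not give.

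**The case against.** The strongest reply is that the trial is plainly meant for patients after surgery in the adjuvant setting. Item 1 requires surgery, recruitment is from a breast surgery department, the Significance section discusses adjuvant endocrine therapy and early disease, the effect assumption is a reduction in recurrence, and the form records a recurrence time. The trial is single-centre, so different sites reading the list differently is not an issue. All this stands, and it makes substantial enrolment of stage IV patients less plausible. It does not supply the criterion: eligibility is decided by the list, and the intended population was not carried into it.

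The second reply is that the size is wholly assumed and, on the absolute scale that the plan uses, small: 10 to 9.5 points at 5%. That is also fair. The relative-risk figures look larger but depend on the chosen 20% v 10%.

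A reader might go further in four ways that the documents do not support.

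- *Such patients are being randomised.* The text shows only that they can be.
- *The M field shows that M1 patients were expected.* T, N and M are ordinary staging fields, and recording M says little about who was meant to enter.
- *The progression wording proves an advanced-disease population.* It may be loose drafting, and the point does not need it.
- *Anyone with a past recurrence can never be disease-free.* A patient whose local recurrence was completely removed can be disease-free at randomisation. The problem is disease present at that time, not any history of recurrence.

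Removal after randomisation is likewise a risk rather than a stated plan. No section provides for it on this ground, although exclusions 12 and 13 already describe conditions that can arise only after treatment has begun.

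**Conclusion.** The point holds as an inconsistency between a stated entry rule and the primary endpoint. Followed as written, the criteria admit patients whose DFS event has already occurred or cannot be dated from randomisation, and no other section closes the gap. The omission is certain on the text.

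Its effect is not. Neither the control DFS rate nor the proportion affected is given, and that proportion may be small. The 9.7 to 9.0 points and the relative risks of 0.57 to 0.68 rest on assumed rates of 20% v 10%, on 3% to 10% of patients being affected equally in both arms, and on counting all of them as events. They show direction and order of size only. The missing DFS event list and time origin are a related gap, and this point does not settle which events should count.

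**What to change.** Amend inclusion 1 to require M0 disease, completed curative-intent surgery, and no known local, regional or distant disease of the index cancer at randomisation. Judge this from the TNM, pathology and surgery data already on the form and from the medical-record review already planned at recruitment. No new procedure is needed. The limit of this approach is that it will not detect a recurrence that nobody has yet diagnosed. There is no need to change the accepted means of confirming the diagnosis or to bar every past recurrence.

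For patients already enrolled, identify those not disease-free at entry from pre-randomisation data only, by a written rule fixed before outcomes are compared between arms. This keeps the classification independent of allocation and outcome.

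The progression wording in Overview of design and the DFS endpoint in Measurements must be reconciled so that the two sections describe the same kind of patient. No stopping rule is proposed here.

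The cost is protocol wording and a short written rule. The downside is small: a few stage IV or currently recurrent patients would be screened out.

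### On its natural reading, the diabetic clause of exclusion 6 excludes no diabetic aged 40 to 75, contrary to the exclusion's purpose, and its wording also allows an opposite reading

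*Combined protocol and SAP*

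**What the plan says.** All eligibility text is in the Combined protocol and SAP under Study subjects.

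- The population is defined by risk class: "Target population: Breast cancer patients with dyslipidemia (low and medium risk of ASCVD".
- Inclusion 2 sets the entry age: "Female patients (35-75 years old".
- Inclusion 3 asks for "The low-risk patients with ASCVD", without defining low risk.
- Exclusion 6 is headed "High-risk ASCVD patients (in accordance with one of the following circumstances", so any single listed circumstance is enough to exclude.
- One circumstance applies at any age: "LDL-C > 4.9 mmol/L or TC > 7.2 mmol/L".
- The diabetic clause follows: "Diabetic patients with 1.8 mmol/L < LDL-C < 4.9 mmol/L (or) 3.1 mmol/L < TC < 7.2 mmol/L and age < 40 years". The part at issue is its ending, "3.1 mmol/L < TC < 7.2 mmol/L and age < 40 years".
- A further clause covers women under 55 at moderate 10-year risk who have two or more listed risk factors.

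Exclusion 5 removes established ASCVD and exclusion 8 removes uncontrolled diabetes, both at any age. In the Significance section the plan reports that "cardiovascular events in breast cancer patients aged over 66 were the leading cause of death".

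**The concern.** The age condition points in an unexpected direction for a rule meant to remove high-risk patients. Of two diabetic women with the same lipids, one aged 38 and one aged 68, the clause excludes the younger and passes the older. The plan gives no reason for this, and its own background describes cardiovascular risk as rising after menopause.

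Two things are at stake. First, women whom exclusion 6 may have been written to keep out could be enrolled. With 1:1 allocation, about half of them would be assigned to dietary intervention in place of a statin. Risk class matters within this plan, because the Significance section cites different LDL-C targets for low, medium and high risk (4.1, 3.4 and 2.6 mmol/L). Second, the result is meant to apply to low- and medium-risk patients, and that description depends on the exclusion working as intended.

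**Working it through.** The point concerns eligibility logic, so there is no planned figure to reproduce. The check applies the diabetic clause at each whole year of age from 35 to 75.

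**Number of ages.** 75 - 35 + 1 = 41 one-year ages. Ages 35-39 are 5 of them (5/41 = 12.2%). Ages 40-75 are 36 (36/41 = 87.8%). These are shares of age values, not of patients.

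**Two ways to group the clause.**

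- Reading A, the natural one: (LDL-C in range OR TC in range) AND age < 40.
- Reading B: LDL-C in range OR (TC in range AND age < 40).

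Results for a diabetic woman, with illustrative lipid values in mmol/L:

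| LDL-C | TC | Reading A excludes | Reading B excludes |
|---|---|---|---|
| 3.5 | 5.5 | ages 35-39 (5 of 41) | ages 35-75 (41 of 41) |
| 1.5 | 5.5 | ages 35-39 (5 of 41) | ages 35-39 (5 of 41) |
| 1.5 | 3.0 | none | none |

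In the first row, where both lipids are in range, the two readings give opposite decisions at all 36 ages from 40 to 75.

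**Do other criteria close the gap under reading A?** Take a woman aged 55-75 with controlled diabetes, LDL-C 3.5, TC 5.5, no established ASCVD and no other excluding condition.

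- Exclusion 6, LDL-C above 4.9 or TC above 7.2: not met.
- Exclusion 6, moderate risk with two or more factors: limited to women under 55, so it cannot apply.
- Exclusion 5: needs established disease, so not met.
- Exclusion 8: needs uncontrolled diabetes, so not met. Naming only uncontrolled diabetes suggests that other diabetics may enter.
- Inclusion 3: asks for low risk but gives no definition. The only worked definition of high risk is exclusion 6 itself, so inclusion 3 is no independent check. It is also narrower than the low- and medium-risk target population.

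No defined criterion stops her. Ages 55-75 are 75 - 55 + 1 = 21 of the 41 ages (51%). At ages 40-54 (15 of 41), only the multi-factor clause might catch an otherwise similar woman.

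**The case against.** The strongest reply is that exclusion 6 does not act alone. A reader might infer that the protocol admits every diabetic aged 40 or more. It does not: very high LDL-C or TC, established ASCVD, uncontrolled diabetes, the under-55 multi-factor clause and inclusion 3 can each remove some of them. This stands, and it limits the point to what the diabetic clause does and to the patients whom no defined criterion reaches.

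A reader might also infer that the clause defeats its purpose and that the trial population is no longer low and medium risk. The documents do not go that far. They nowhere state that diabetics aged 40 or more with these lipids are high risk, and the Significance section speaks of older breast cancer patients in general, not of diabetics. What the text supports is an unexplained inconsistency.

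Third, it is tempting to size the problem with the 69.75% of Chinese breast cancer cases over 45 given under Significance. That figure describes all cases, not diabetics or candidates for this trial, and no diabetes prevalence is given. It should not be used here.

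Fourth, the argument depends on one inequality sign in a block whose layout is visibly broken, and a sign altered when text was extracted from the PDF cannot be ruled out. This is a reason to check the line. It does not settle the matter, because the "and"/"or" grouping would remain unclear whichever way the sign points.

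Finally, randomisation spreads any such patients over both arms. The point therefore bears on eligibility, safety and applicability, and not on bias in the comparison.

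**Conclusion.** The point holds in this limited form. On the natural reading, the diabetic clause of exclusion 6 acts at 5 of the 41 eligible one-year ages and excludes no diabetic aged 40 or more. A woman aged 55-75 with controlled diabetes, in-range lipids and no established ASCVD then meets no defined exclusion. This does not fit the heading of exclusion 6, the stated risk limit or the plan's own background. On the other grouping, a diabetic with LDL-C between 1.8 and 4.9 mmol/L is excluded at every age, so the same patient can be eligible or ineligible depending on who reads the line. Either way the line needs correcting.

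This rests on the inequality sign being as it appears in the text and, for the gap at 55-75, on low risk having no working definition elsewhere. The number of patients affected is unknown and may be small.

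**What to change.** The sponsor should check the age condition in the diabetic clause against the risk definition from which it was taken and against the original document. It should reconcile the condition with the 35-75 entry range and the low- and medium-risk aim, and rewrite the line so that it is clear whether the age condition covers both lipid branches or only one. Which age rule is right is for the sponsor to settle from its source.

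The sponsor should also identify diabetics already enrolled and record how the clause was applied to them. The text change is one line. The listing costs somewhat more: the case form in the Appendix has no field for diabetes, so it means going back to the medical records. That record check is the only real downside.
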